8.8.4. Clinical Safety Laboratory Assessments

- A central laboratory will be used in this study.
- Refer to [Appendix 2](#) for the list of clinical laboratory tests to be performed and to the SoA (Section 1.3) for the timing and frequency.
- The investigator must review the laboratory report, document this review, and record any clinically relevant changes occurring during the study in the AE section of the CRF. The laboratory reports must be filed with the source documents. Clinically significant abnormal laboratory findings are those which are not associated with the underlying disease, unless judged by the investigator to be more severe than expected for the participant's condition.
- All laboratory tests with values considered clinically significantly abnormal during participation in the study or within 60 days after the last dose of study intervention should be repeated until the values return to normal or baseline or are no longer considered significantly abnormal by the investigator or medical monitor.
- If such values do not return to normal/baseline within a period of time judged reasonable by the investigator, the etiology should be identified and the sponsor notified.
- All protocol-required laboratory assessments, as defined in [Appendix 2](#), must be conducted in accordance with the laboratory manual and the SoA.
- Laboratory toxicity will be graded using the Adverse Event and Laboratory Value Severity Grading Table ([Appendix 2](#), Section 10.2.1). The Table is based upon publicly available Tables from the National Institute of Allergy and Infectious Disease Division of Microbiology and Infectious Diseases

(www.niaid.nih.gov) and Common Terminology Criteria for Adverse Events (CTCAE) Version 4.0 ([U.S. Department of Health and Human Services](#), 2010).

- Note: If a laboratory value is reported that requires withholding of further dosing, the site personnel must contact the parent/caregiver promptly to ensure no further injections are administered until reviewed with the investigator if the next administration would be away from the clinic.

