
MONITORING:
 
For bilirubin or INR criteria:
 
 Repeat liver chemistries (include ALT, AST, alkaline phosphatase, bilirubin and INR) and perform liver event follow-up assessments within 24 hrs Monitor participants twice weekly until liver chemistries resolve, stabilize or return to within baseline A specialist or hepatology consultation is recommended 
For All other criteria:
 
 Repeat liver chemistries (include ALT, AST, alkaline phosphatase, bilirubin and INR) and perform liver event follow-up assessments within 24-72 hrs Monitor participants weekly until liver chemistries resolve, stabilize or return to within baseline 	
 Fractionate bilirubin, if total bilirubin $\geq 2 \times \text{ULN}$ Obtain complete blood count with differential to assess eosinophilia Record the appearance or worsening of clinical symptoms of liver injury, or hypersensitivity, on the AE report form Record use of concomitant medications on the concomitant medications report form including acetaminophen, herbal remedies, other over the counter medications. Record alcohol use on the liver event alcohol intake case report form (CRF) page 
For bilirubin or INR criteria:
 
 Anti-nuclear antibody, anti-smooth muscle antibody, Type 1 anti-liver kidney microsomal antibodies, and quantitative total immunoglobulin G (IgG) or gamma globulins. Serum acetaminophen adduct high performance liquid chromatography (HPLC) assay (quantifies potential acetaminophen contribution to liver injury in participants with definite or likely acetaminophen use in the preceding week [James, 2009]). NOTE: not required in China Liver imaging (ultrasound, magnetic resonance, or computerised tomography) and /or liver biopsy to evaluate liver disease: complete Liver Imaging and/or Liver Biopsy CRF forms.
---	---

1. Serum bilirubin fractionation should be performed if testing is available. If serum bilirubin fractionation is not immediately available, discontinue study intervention for that participant if $\text{ALT} \geq 3 \times \text{ULN}$ **and** bilirubin $\geq 2 \times \text{ULN}$. Additionally, if serum bilirubin fractionation testing is unavailable, **record presence of detectable urinary bilirubin on dipstick**, indicating direct bilirubin elevations and suggesting liver injury.

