
ALT \geq5xULN and $<$8xULN and bilirubin $<$2xULN without symptoms believed to be related to liver injury or hypersensitivity, and who can be monitored weekly for 2 weeks.
 
OR
 
ALT \geq3xULN and $<$5xULN and bilirubin $<$2xULN without symptoms believed to be related to liver injury or hypersensitivity, and who can be monitored weekly for 4 weeks.
	
 • Notify the GSK medical monitor within 24 hours of learning of the abnormality to discuss participant safety. • Participant can continue study intervention • Participant must return weekly for repeat liver chemistries (ALT, AST, alkaline phosphatase, bilirubin) until they resolve, stabilise or return to within baseline • If at any time participant meets the liver chemistry stopping criteria, proceed as described above • If ALT decreases from ALT \geq5xULN and $<$8xULN to \geq3xULN but $<$5xULN, continue to monitor liver chemistries weekly. • If, after 4 weeks of monitoring, ALT $<$3xULN and bilirubin $<$2xULN, monitor participants twice monthly until liver chemistries normalize or return to within baseline.

References

Le Gal F, Gordien E, Affolabi D, Hanslik T, Alloui C, Dény P, et al. Quantification of hepatitis delta virus RNA in serum by consensus real-time PCR indicates different

patterns of virological response to interferon therapy in chronically infected subjects.
J Clin Microbiol. 2005;43(5):2363–2369.

10.5.1. Restart Following Transient Resolving Liver Stopping Events Not Related to Study Intervention

After liver stopping criteria are met, restart or rechallenge is not permitted, see Section 7.1.2.1.

10.6. Appendix 6: Medical Device Incidents: Definition and Procedures for Recording, Evaluating, Follow-up, and Reporting

Definition and Documentation of Medical Device Incidents

Definitions of a Medical Device Incident

The detection and documentation procedures described in this protocol apply to all GSK medical devices provided for use in the study (see Section 6.1 for the list of GSK medical devices).

Medical Device Incident Definition

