8.2.5. Immunoglobulin Levels Below LLN by Visit

The number and percentage of subjects with immunoglobulin values (IgG, IgA, and IgM) below the LLN at each visit will be presented for all subjects [T3.39]. No statistical tests will be performed.

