13. APPENDICES

13.1. Appendix 1: Assessment Windows

13.1.1. Definitions of Assessment Windows for Analyses

The data is analysed as per the planned visit assignment.

Exit/withdrawal and unscheduled visits will be slotted to the appropriate planned visit. The assigned visit is based on the interval in which the Study Day for the exit/withdrawal or unscheduled visit falls according to intervals (inclusive) provided below. For completeness, the table also includes visits which are not slotted; these visits will have 'N/A' for 'not available' listed for the Interval Start and End Day.

Analysis	Parameter	Target ¹	Analysis	Analysis Window		Analysis Timepoint
Set / Domain	(if applicable)		Beginning Timepoint	Ending Timepoint	Timepoint Number	
All	NA	Day -35	N/A	N/A	10	Screening
Cohort 1 ar	d Cohort 3	_L			I.	
All	All	Day 1	N/A	N/A	20	Week 0 (Day 1)
		Day 8	2	11	30	Week 1 (Day 8/11)
		Day 15	12	21	40	Week 2 (Day 15/21)
		Day 29	22	42	50	Week 4 (Day 29/31)
		Day 57	43	70	60	Week 8 (Day 57/61)
		Day 85	71	98	70	Week 12 (Day 85/81)
		Day 113	99	126	80	Week 16
		Day 141	127	154	90	Week 20
		Day 169	155	189	100	Week 24
		Day 211	190	231	110	Week 30
		Day 253	232	280	120	Week 36
		Day 309	281	336	130	Week 44
		Day 365	337	378	140	Week 52
		Day 421	N/A	N/A	175	8 Week Follow-up ²
		Day 477	N/A	N/A	185	16 Week Follow-up ³
Cohort 2						
All	All	Day 1	N/A	N/A	20	Week 0 (Day 1)
		Day 11	2	15	30	Week 1 (Day 8/11)
		Day 21	16	25	40	Week 2 (Day 15/21)
		Day 31	26	45	50	Week 4 (Day 29/31)
		Day 61	46	70	60	Week 8 (Day 57/61)
		Day 81	71	96	70	Week 12 (Day 85/81)
		Day 113	97	126	80	Week 16
		Day 141	127	154	90	Week 20
		Day 169	155	189	100	Week 24

CONFIDENTIAL

200908

Analysis Parameter Set / (if Domain applicable)		Target ¹	Analysis Window		Analysis	Analysis Timepoint
			Beginning Timepoint	Ending Timepoint	Timepoint Number	
		Day 211	190	231	110	Week 30
		Day 253	232	280	120	Week 36
		Day 309	281	336	130	Week 44
		Day 365	337	378	140	Week 52
		Day 421	N/A	N/A	175	8 Week Follow-up ²
		Day 477	N/A	N/A	185	16 Week Follow-up ³

Note:

¹ Study Day with Baseline/Treatment Start Date as Day 1.

²The 8-week follow-up occurs 8 weeks after Week 52, or 8 weeks after early withdrawal or 8 weeks after last dose for subjects who withdraw from Part A and do not enter Part B.

³ The 16-week follow-up occurs 16 weeks after Week 52, or 16 weeks after early withdrawal or 16 weeks after last dose for subjects who withdraw from Part A and do not enter Part B.

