13.4. Appendix 4: Derived and Transformed Data

13.4.1. General

Multiple Measurements at One Analysis Time Point

- For continuous data, if there are two values within a time window (as per Section 13.1.1) the value closest to the target day for that window will be used. If values are the same distance from the target, then the mean will be taken. All data will be presented in the listings.
- For categorical data, if there are two values within a time window (as per Section 13.1.1) the value closest to the target day for that window will be used. If values are the same distance from the target, then the value prior to the target day will be taken. All data will be presented in the listings.
- Participants having both High and Low values for Normal Ranges at any post-baseline visit for safety parameters will be counted in both the High and Low categories of "Any visit post-baseline" row of related summary tables.

Study Day

- Calculated as the number of days from First Dose Date:
 - Ref Date = Missing → Study Day = Missing
 - Ref Date < First Dose Date → Study Day = Ref Date First Dose Date
 - Ref Date ≥ First Dose Date → Study Day = Ref Date First Dose Date + 1

Study Completion

- A participant is considered to have completed the primary study if he/she has completed all phases during Parts A and B of the study, including the Week 52 Visit, as defined in the Schedule of Activities (SoA) Section 1.3 of the protocol.
- A participant is considered to have completed Part A of the study if he/she has completed all 12
 weeks of the treatment phase, including the Week 12 Visit, as defined in the SoA (see Section 1.3 of
 the protocol).
- Participants who withdraw from study treatment prior to the end of Part A and participants who
 complete Part A but do not wish to continue into Part B are required to complete 8 and 16 week
 follow-up visits.
- Participants who withdraw from treatment prior to Week 12, should complete an early withdrawal (EW) visit, in addition to the 8 and 16 week follow-up visit and assessments. The EW visit requires identical assessments and procedures to the Week 12 (Day 85/81) visit.
- Participants who withdraw from treatment prior to Week 52, should complete an EW visit, in addition to the 8 and 16 week follow-up visit and assessments. The EW visit requires identical assessments and procedures to the Week 52 visit.

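### In by-visit laboratory summaries, a repeat taken because of an abnormal result can displace the scheduled value, mainly in Part B

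*SAP*

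**What the plan says.** SAP 13.1.1 begins by saying that data are analysed by planned visit, and then adds: "Exit/withdrawal and unscheduled visits will be slotted to the appropriate planned visit". Assignment is by study day, "according to intervals (inclusive) provided below". From the first post-baseline visit to Week 52 the windows are contiguous. Week 16 in Cohorts 1 and 3, for example, covers Days 99–126 around Day 113, and Week 44 covers Days 281–336 around Day 309.

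For two values in one window, SAP 13.4.1 states that "the value closest to the target day for that window will be used". For continuous data it adds: "If values are the same distance from the target, then the mean will be taken". It does not distinguish a scheduled value from an unscheduled one, and it does not cover three or more values.

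Protocol 8.8.4 says that clinically significantly abnormal tests "should be repeated until the values return to normal or baseline", or until the investigator or medical monitor no longer considers them significantly abnormal. The same section generally limits clinical significance to findings not associated with the underlying disease, unless they are more severe than expected. Protocol Appendix 5 sets its own timing for liver tests. For most stopping criteria the site is to repeat the chemistries and "perform liver event follow-up assessments within 24-72 hrs"; for the monitoring criteria, "Participant must return weekly for repeat liver chemistries".

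**The concern.** The nearest-to-target rule does not look at the result, but the existence of a second value does depend on it. A participant with an unremarkable scheduled test contributes one value to the window. A participant with a clinically significant abnormality contributes that value and one or more repeats, and the repeating stops once the test has improved or is no longer considered significant. If the rule then picks a repeat, the by-visit summary mixes scheduled values with values obtained for cause. On average the mix leans toward normal.

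The outputs chiefly exposed are the by-visit summaries and mean plots for hematology, liver function, electrolytes and other chemistries (T3.18–T3.21, F3.01–F3.04). T3.39, which counts immunoglobulin values "below the LLN at each visit will be presented for all subjects", may also be exposed. IgG has toxicity-grade tables in SAP Table 5 but IgA and IgM do not, so for those two no graded table would offset a displaced value.

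**Working it through.** The plan states no figure on this point, so there is nothing to reproduce. The check applies the SAP rule to the visit tolerances.

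**Inputs**
- Visit tolerance: ±2 days in Part A and ±7 days in Part B (Protocol 1.3).
- Windows: SAP 13.1.1. Selection and tie rules: SAP 13.4.1.
- Assumed, because the documents do not give them: scheduled visits spread evenly over the tolerance, and the lag from scheduled value to repeat.

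**When a repeat wins.** Let the scheduled visit fall d days before target and the repeat come L days later. The distances from target are d and |L − d|. The repeat is used if |L − d| < d, that is, for L from 1 to 2d − 1. At L = 2d the two are equidistant and a continuous value is averaged. If the scheduled visit is on or after target, its own later repeat is always further away and never displaces it. The longest winning lag is 2×2 − 1 = 3 days in Part A and 2×7 − 1 = 13 days in Part B.

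Examples at Week 16 (target Day 113):
- Scheduled Day 108, repeat Day 113: the repeat is used.
- Scheduled Day 113, repeat Day 116: the scheduled value is used.
- Scheduled Day 118, repeat Day 121: the scheduled value is used.

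**How often, at a fixed lag.** A repeat at lag L wins if d ≥ (L + 1)/2. There are 15 possible offsets in Part B and 5 in Part A.

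| Lag | d needed | Part B | Part A |
|---|---|---|---|
| 3 days | ≥ 2 | 6/15 = 40% | 1/5 = 20% |
| 5 days | ≥ 3 | 5/15 = 33% | 0/5 = 0% |
| 7 days | ≥ 4 | 4/15 = 27% | 0/5 = 0% |

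**How often, with the lag spread evenly over a range**

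| Lag range | Part B | Part A |
|---|---|---|
| 1–3 days | 19/45 = 42.2% | 4/15 = 26.7% |
| 1–7 days | 37/105 = 35.2% | 4/35 = 11.4% |
| 1–14 days | 49/210 = 23.3% | 4/70 = 5.7% |

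A further 2–3% (Part B) or 3–7% (Part A) would be averaged. All these percentages are conditional on there being an abnormal scheduled value and a repeat of it.

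**Effect on the summary.** A simulation used a standard normal analyte, 10% or 20% abnormal at the scheduled visit, within-subject correlation 0.5 or 0.8, exactly one repeat for every abnormal value, and the lag ranges above.

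| Scheduled abnormal rate | Reported, Part B | Reported, Part A |
|---|---|---|
| 10% | 7.0–8.9% | 7.8–9.7% |
| 20% | 15.1–18.2% | 16.5–19.4% |

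The mean moved toward normal by 0.003 to 0.06 SD. With 28 participants, one person is 1/28 = 3.6 percentage points. The largest Part B drops are 3.0 points (0.030 × 28 = 0.8 of a participant) and 4.9 points (0.049 × 28 = 1.4 participants), even if all 28 entered the optional Part B.

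**The case against.** The strongest reply is that the rule is prespecified, ignores the result, and respects planned timing, which SAP 13.3.2 uses for summaries. It can also substitute a worse repeat. Nothing is hidden. The worst-grade and grade-worsening tables (8.2.2, 8.2.3) include unscheduled values, the any-time proteinuria rows (7.2.1) count any high value among participants normal at baseline, and all laboratory results are listed. The study is descriptive, and by-visit and worst-case tables answer different questions. Giving the scheduled value absolute priority would also have a cost: Protocol Section 8 allows repeats for technical problems with a sample, and a suspect scheduled result should not beat its valid replacement.

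Most of this stands and limits the point. It does not answer the central issue: the rule ignores the result, but the set of values it chooses from does not. Nor do two other sentences in the SAP close the gap. The opening of 13.1.1 is followed at once by the slotting rule, and the statement in 13.3.2 that unscheduled visits appear in listings does not confine them to listings.

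A reader might go further and infer that proteinuria shifts (T2.04) and the biomarker tables (T4 series), including the secondary endpoint, are materially distorted. The documents do not support that. Protocol 8.8.4 generally leaves out abnormalities associated with lupus, and falls in B cells and immunoglobulins are an expected effect of belimumab (Protocol 2.2.1.3), so mandated repeats give only weak exposure there. Nor is the primary endpoint touched by this route, since belimumab concentration is not a test repeated for abnormality.

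**Conclusion.** The point holds as a minor one. As written, SAP 13.1.1 and 13.4.1 allow a for-cause repeat to replace the scheduled abnormal value in by-visit safety laboratory summaries. The scheduled visit must have been early, so this is mainly a Part B matter: 27–40% of repeats at lags of 3 to 7 days, against 20% at 3 days and none at 5 or 7 days in Part A. Those figures rest on evenly spread visits. The documents give no abnormality rates, repeat counts or actual lags, so the overall effect cannot be stated. Under assumptions that have every abnormal value repeated, it is about one participant per visit. The pull toward normal is an average tendency, not a certainty for any one participant. Graded abnormal results stay in the worst-grade and grade-worsening tables, and every result stays in the listings.

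**What to change.** Add to SAP 13.4.1: for by-visit summaries and figures, the value from the scheduled visit takes priority; an unscheduled or exit value is used only if the scheduled value is missing or its sample was technically invalid. Unscheduled values stay in the listings and in the worst-post-baseline and grade-worsening tables, as 8.2.2 and 8.2.3 already provide.

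This removes replacement by for-cause repeats of valid scheduled values. It also settles three or more values in a window whenever a valid scheduled value exists. The cost is one sentence and one sort key in programming. The downside is that a scheduled value further from target will sometimes be kept over a nearer unscheduled one.

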13.4.2. Study Population

Age Derivation

If the day of date of birth is unavailable, age on any specified day (e.g. screening, 1st dose etc.) will be derived as:

If the specified day is on or after the 15th of the birth month then:

Year of specific timepoint – DOB year

If the specified day is before the 15th of the birth month then:

(Year of specific timepoint – DOB year) - 1

Age at screening will be defined as the screening date, and derived as above.

Age Derivation

Extent of Exposure

- Number of days of exposure to study drug will be calculated based on the formula:

 Duration of Exposure in Days = Treatment Stop Date (Treatment Start Date) + X,
 where X is 7, 10, or 14 for the three weight cohorts respectively.
- Only complete dates will be used when calculating duration of exposure. First and last injection dates will be used, regardless of any missing doses.
- Participants who were enrolled but did not report a treatment start date will be categorised as having zero days of exposure.

13.4.3. SELENA SLEDAI

SELENA SLEDAI assessment

The SELENA SLEDAI assessment consists of 24 individual weighted items in which signs and symptoms, laboratory tests, and physician's assessment for each of 8 organ systems are given a weighted score and summed if present (marked 'Yes') at the time of the visit or in the preceding 10 days.

The SELENA SLEDAI total score is calculated by adding the weighted scores together for all items that are present. If any item is missing, the SELENA SLEDAI total score will be missing.

The maximum theoretical score is 105 (all 24 descriptors present simultaneously) with 0 indicating inactive disease (marked 'No').

Organ System	Descriptor	Weight
CNS	Seizure	8
	Psychosis	8
	Organic Brain Syndrome	8
	Visual Disturbance	8
	Cranial Nerve Disorder	8
	Lupus Headache	8
	CVA ¹	8
Vascular	Vasculitis	8
Musculoskeletal	Arthritis	4
	Myositis	4
Renal	Urinary Casts	4
	Hematuria	4
	Proteinuria	4
	Pyuria	4
Mucocutaneous	Rash	2
	Alopecia	2
	Mucosal Ulcers	2

SELENA SLEDAI assessment				
Cardiovascular and Respiratory	Pleurisy Pericarditis	2 2		
Immunologic	Low Complement Increased DNA Binding	2 2		
Constitutional	Fever ¹	1		
Hematologic	Thrombocytopenia Leukopenia	1		

¹ In the analysis of SELENA SLEDAI by organ systems and items (baseline, improvements, and worsening), CVA will be moved from the CNS to the Vascular organ system and the Constitutional organ system will be eliminated and its one component, fever, will be moved to the hematologic organ system.

13.4.4. Prednisone Equivalent Conversion

- A concomitant medication is identified as a steroid if at least one associated ATC code (ATCCD1 ATCCD6) begins with 'H02.' Mineralocorticords are included in the group of ATC codes beginning with 'H02' but do not have sufficient anti-inflammatory properties to be considered as a prednisone equivalent. For this reason, the conversion factor has been set to 0.
- The following routes are considered to provide systemic exposure: oral, buccal, parenteral, subcutaneous, intramuscular, intradermal, and intravenous. Although not systemic, intra-articular steroids are also identified for treatment failure rules. Topical routes of administration are excluded (e.g., topical, conjunctival, intranasal).
- At database lock, all preferred terms identified with an ATC code beginning with 'H02' will be reviewed to ensure a conversion factor exists for all terms with a systemic route of administration.
- Similarly, all routes of administration for preferred terms with an ATC code beginning with 'H02' will be reviewed to ensure all systemic routes have been identified in the list below.
- In order to be converted, the frequency and dose of the steroid must be present with the unit dose in milligrams (mg) or grams (g). Doses recorded in grams will be converted to milligrams by multiplying the dose in grams by 1000 prior to applying the conversion factor.
- Reported dose for systemic steroid is converted to prednisone equivalent dose using conversion factor for each particular medication (refer to online calculator http://www.globalrph.com/corticocalc.htm).

Prednisone Equivalent	= Collected	x Conversion	x Frequency
Daily Dose (mg)	Dose (mg)	Factor	Factor

Prednisone Conversion Factors (mg)	
	Conversion factor for converting to a
Preferred term	prednisone-equivalent dose
BETAMETHASONE	8.3333`
BETAMETHASONE DIPROPIONATE	8.3333`
BETAMETHASONE SODIUM PHOSPHATE	8.3333`
BETROSPAM	8.3333`
BUDESONIDE	0.3333`
CORTISONE	0.2
CORTISONE ACETATE	0.2
CRONOLEVEL	8.3333`
DEFLAZACORT	0.8333`
DEXAMETHASONE	6.6666`
DEXAMETHASONE ACETATE	6.6666`
DEXAMETHASONE SODIUM PHOSPHATE	6.6666`
FLUDROCORTISONE	0
FLUOCORTOLONE	3
HYDROCORTISONE	0.25
HYDROCORTISONE ACETATE	0.25
HYDROCORTISONE SODIUM SUCCINATE	0.25
MEPREDNISONE	1.25
METHYLPREDNISOLONE	1.25
METHYLPREDNISOLONE ACETATE	1.25
METHYLPREDNISOLONE SODIUM SUCCINATE	1.25
PARAMETHASONE	2.5
PREDNISOLONE	1
PREDNISOLONE ACETATE	1
PREDNISOLONE SODIUM PHOSPHATE	1
PREDNISOLONE SODIUM SUCCINATE	1
PREDNISONE	1
PREDNISONE ACETATE	1
TRIAMCINOLONE	1.25
TRIAMCINOLONE ACETATE	1.25
TRIAMCINOLONE ACETONIDE	1.25

Combination Products: Prednisone Conversion Factors (mg)				
		Conversion factor for converting to a prednisone-		
Preferred term	Ingredients	equivalent dose		
CELESTONA BIFAS	Betamethasone acetate +	8.3333`		
	Betamethasone sodium phosphate			
DEPO-MEDROL MED LIDOKAIN	Methylprednisolone + Lidocaine	1.25		

CELESTAMINE	Betamethasone +	8.3333`
	Dexchlorpheniramine maleate	
SYNBETAMINE	Betamethasone +	8.3333`
	Dexchlorpheniramine maleate	

